7.2. Participant Discontinuation/Withdrawal From the Study

A participant may withdraw from the study at any time at his/her own request. Reasons for discontinuation from the study include the following:

- Refused further follow-up;
- Lost to follow-up;
- Death;
- Study terminated by sponsor;
- AEs;
- Parent(s)/legal guardian or participant request;

- Protocol violation.

If a participant does not return for a scheduled visit, every effort should be made to contact the participant's parent(s)/legal guardian. All attempts to contact the parent(s)/legal guardian and information received during contact attempts must be documented in the participant's source document. In any circumstance, every effort should be made to document participant outcome, if possible.

The parent(s)/legal guardian should be questioned regarding the reason for the participant's withdrawal. The investigator or his or her designee should capture the reason for withdrawal in the CRF for all participants.

If a participant withdraws from the study, his/her parent(s)/legal guardian may request destruction of any remaining samples taken and not tested, and the investigator must document any such requests in the site study records and notify the sponsor accordingly.

The parent(s)/legal guardian should be requested to have the participant return for a final visit, if applicable, and the investigator will perform the procedures indicated for the next visit. Any AEs or SAEs that are continuing at the time of withdrawal from the study should be followed until resolution or, in case of permanent impairment, until the condition stabilizes.

A final telephone contact 6 months after the last vaccination ([Section 8.11.3](#)) for the collection of safety information should be completed for all participants who withdraw or have been withdrawn within 6 months after administration of study intervention, unless consent for further contact has been withdrawn or the participant is lost to follow-up.

Participant withdrawal should be explained in the source documents and should include whether the withdrawal is only from further receipt of study intervention or also from study procedures and/or postvaccination study follow-up.

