8.11.3. Final Telephone Contact for Participants Who Withdraw From the Study

- This telephone contact should occur if a participant withdraws or is withdrawn from the study within 6 months after Vaccinations 1 and 2, or within 1 month after Vaccination 3; this contact should be attempted for all participants who have withdrawn from the study within the specified timeframe after receiving any study vaccination, unless they have withdrawn consent.
- Contact the parent(s)/legal guardian or the participant by telephone.
- Complete the Study Visit/Telephone Contact AE Checklist to:
 - Inquire whether the participant had any NDCMCs since the last visit. Inquire whether the participant had any of the following related to an AE since the last visit: hospitalizations, visits to other medical facilities, medication use, or missed days of school or work. Please refer to the ISF for additional details.
 - Inquire about neuroinflammatory and autoimmune conditions, such as transverse myelitis, uveitis, optic neuritis, and multiple sclerosis. Please refer to the ISF for additional details.
- Report any SAEs to the sponsor as defined in [Section 8.3](#).
- Record AEs as described in [Section 8.3](#) and the [SoA](#).
- Record concomitant medications used to treat AEs as described in [Section 6.5](#).
- Review AEs that were ongoing since the previous visit, and record their end dates or confirm that they are still continuing.
- Record nonstudy vaccinations as described in [Section 6.5](#).
- Complete the source documents.
- Complete the CRFs.

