## 2.1.4. Primary Estimands

- **Primary Immunogenicity Estimands**

For the first objective (to describe the immune response for MenB induced by 2 doses of MenABCWY administered on a 0- and 12-month schedule), the primary estimand has the following attributes:

- Population: Participants receiving 2 doses of MenABCWY and who are in compliance with the key protocol criteria (evaluable participants).
- Variable: hSBA titer for each of the primary MenB test strains (A22, A56, B24, and B44).
- Intercurrent event(s): Participants will be summarized according to the vaccine group to which they were randomized. Missing serology data will not be imputed.
- Population-level summary: The percentage of participants achieving an hSBA titer  $\geq$  LLOQ (1:16 for strain A22 and 1:8 for strains A56, B24, and B44) for each of the 4 primary MenB test strains at baseline and 1 month after the second dose of MenABCWY in Group 1 (0- and 12-month schedule).

For the second objective (to describe the immune response for MenB induced by 2 doses of MenABCWY administered on a 0- and 36-month schedule), the primary estimand has the following attributes:

- Population: Participants receiving 2 doses of MenABCWY and who are in compliance with the key protocol criteria (evaluable participants).
- Variable: hSBA titer for each of the primary MenB test strains (A22, A56, B24, and B44).
- Intercurrent event(s): Participants will be summarized according to the vaccine group to which they were randomized. Missing serology data will not be imputed.
- Population-level summary: The percentage of participants achieving an hSBA titer  $\geq$  LLOQ (1:16 for strain A22 and 1:8 for strains A56, B24, and B44) for each of the 4 primary MenB test strains at baseline and 1 month after the second dose of MenABCWY in Group 2 (0- and 36-month schedule).

The planned analyses for the primary endpoints as related to the estimands are outlined in [Section 6.1](#).

- **Primary Safety Estimands**

For the primary safety objective to describe the safety profile of MenABCWY when administered on a 0- and 12-month and 0- and 36-month schedule as measured by AEs, SAEs, MAEs, NDCMCs, and immediate AEs, the estimand has the following attributes:

- Population: Participants receiving at least 1 dose of study intervention.
- Variable: AEs, SAEs, MAEs, NDCMCs, and immediate AEs.

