- Intercurrent event(s): Participants will be analyzed according to the vaccine they actually received. Missing AE dates will be handled according to the Pfizer safety rules.
- Population-level summaries:
  - The percentage of participants reporting at least 1 AE, at least 1 SAE, at least 1 MAE, and at least 1 NDCMC during the following time periods:
    - 30 Days after each vaccination.
    - 30 Days after any MenABCWY vaccination.
    - During the Vaccination 1, 2, and 3 vaccination phases:
      - From Vaccination 1 (Visit 1) through 1 month after Vaccination 1 (Visit 2) in Groups 1 and 2.
      - From Vaccination 2 (Visit 4) through 1 month after Vaccination 2 (Visit 5) in Groups 1 and 2.
      - From Vaccination 3 (Visit 9) through 1 month after Vaccination 3 (Visit 10) in Group 2.
  - The percentage of participants reporting at least 1 SAE, at least 1 MAE, and at least 1 NDCMC during the following time periods:
    - During the follow-up phases:
      - From 1 month after Vaccination 1 (Visit 2) through 6 months after Vaccination 1 (Visit 3) in Groups 1 and 2.
      - From 1 month after Vaccination 2 (Visit 5) through 6 months after Vaccination 2 in Groups 1 and 2.

- 6 Months after Vaccinations 1 and 2:
  - From Vaccination 1 (Visit 1) through 6 months after Vaccination 1 (Visit 3) in Groups 1 and 2.
  - From Vaccination 2 (Visit 4) through 6 months after Vaccination 2 in Groups 1 and 2.
- The percentage of participants reporting at least 1 immediate AE after each vaccination.

For the primary safety objective to describe the safety profile of MenABCWY when administered on a 0- and 12-month and 0- and 36-month schedule as measured by days missing school or work because of AEs, the estimand has the following attributes:

- Population: Participants receiving at least 1 dose of study intervention.
- Variable: Days missing from school or work because of AEs.
- Intercurrent event(s): Participants will be analyzed according to the vaccine they actually received. Missing AE dates will be handled according to the Pfizer safety rules.
- Population-level summary: The percentage of participants who missed days of school and/or work because of AEs occurring within 6 months after Vaccinations 1 and 2 and within 1 month after Vaccination 3.

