	
5. Had at least 1 valid and determinate MenA/C/W/Y or MenB assay result at 1 month after the second MenABCWY vaccination (Visit 5 for Group 1 and Visit 10 for Group 2).
 
6. Had received no prohibited vaccines or treatment through Visit 5 (Group 1) or Visit 10 (Group 2).
 
7. Had no important protocol deviations through Visit 5 (Group 1) or Visit 10 (Group 2).

Post-Vaccination 1 mITT population	All participants who received at least 1 study vaccination and had at least 1 valid and determinate MenB or MenA/C/W/Y assay result available at any time point from Visit 1 to Visit 2.
Post-Vaccination 2 mITT population	All participants who received at least 1 study vaccination and had at least 1 valid and determinate MenB or MenA/C/W/Y assay result available at any time point from Visit 1 to Visit 5 for Group 1 and from Visit 1 to Visit 10 for Group 2.
Vaccination 1 safety population	This population will include participants who received the first dose of study intervention at Visit 1 and for whom safety information from Visit 1 up to Visit 4 is available in Groups 1 and 2.
Vaccination 2 safety population	This population will include participants who received the second dose of study intervention at Visit 4 (MenABCWY for Group 1, saline for Group 2) and for whom safety information from Visit 4 up to Visit 7 (for Group 1) or Visit 9 (for Group 2) is available.
Vaccination 3 safety population	This population will include participants who received the third dose of study intervention at Visit 9 (MenABCWY for Group 2) and for whom safety information from Visit 9 through Visit 10 is available.
Follow-up safety population 1	This population will include participants who received the first dose of study intervention and for whom safety information from Visit 2 up to Visit 4 in Groups 1 and 2 is available.
Follow-up safety population 2	This population will include participants who received the second dose of study intervention (MenABCWY for Group 1, saline for Group 2) and for whom safety information from Visit 5 up to Visit 7 (for Group 1) or Visit 9 (for Group 2) is available.

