For determination of the evaluable population(s), items 1 through 5 will be computerized checks of the data, while items 6 and 7 will be determined by clinical review. An important protocol deviation is a protocol deviation that, in the opinion of the sponsor's global medical monitor, would materially affect assessment of immunogenicity, eg, participant receipt of a prohibited vaccine or medication that might affect immune response or a medication error with suspected decrease in potency of the vaccine. The global medical monitor from the sponsor will identify those participants with a protocol deviation prior to unblinding of the study.

For participants withdrawn early, they will be included in the respective follow-up population, in case they have any type of AEs in the respective AE follow-up intervals.

For Analysis 1 (per [Section 7.1](#)), the post-Vaccination 1 evaluable population will be fully defined for both Groups 1 and 2. Similarly, the post-Vaccination 2 evaluable population will be fully defined for Group 1 for Analysis 1. The final determination of the protocol

deviations, and hence the post-Vaccination 2 evaluable population for Group 2, will be completed for the final analysis.

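### The SAP's early-withdrawal sentence can make the follow-up safety denominators (Table 5, Intervals 8 and 9) depend on having an AE; the wording is ambiguous and the effect small, but it should be replaced

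*SAP*

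**What the plan says.** The population table in SAP Section 4 admits to follow-up safety population 1 those who received the first dose and "for whom safety information from Visit 2 up to Visit 4 in Groups 1 and 2 is available". For population 2 it admits those who received the second dose and "for whom safety information from Visit 5 up to Visit 7 (for Group 1) or Visit 9 (for Group 2) is available". Neither definition mentions an AE.

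Below the table, one sentence deals with early withdrawals: "they will be included in the respective follow-up population, in case they have any type of AEs in the respective AE follow-up intervals". No other sentence in Section 4 addresses them. SAP Table 5 uses the two populations for Intervals 8 and 9 only, and gives early withdrawals their own interval start, again with no AE condition.

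The primary safety estimand in SAP 2.1.4 has as its population "Participants receiving at least 1 dose of study intervention". It names the follow-up phases among its summaries, for example "From 1 month after Vaccination 2 (Visit 5) through 6 months after Vaccination 2 in Groups 1 and 2".

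Protocol 7.2 provides a final safety call that "should be completed for all participants who withdraw or have been withdrawn within 6 months after administration of study intervention", with the exception "unless consent for further contact has been withdrawn or the participant is lost to follow-up". Protocol 8.11.3 says that "this contact should be attempted for all participants who have withdrawn from the study within the specified timeframe after receiving any study vaccination".

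**The concern.** A denominator for an event percentage should not be chosen by whether the event occurred. SAEs, MAEs and NDCMCs are all AEs. If early withdrawals enter only when they have an AE, those with an event are counted and those without are left out.

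The Interval 8 and 9 percentages and their Clopper-Pearson intervals belong to the primary safety estimand. SAP 5.2.1.2 says the safety intervals will help decide which events need further clinical investigation. Two programmers could follow Section 4 faithfully and arrive at different values of N. The printed n and N would not show that entry had depended on an AE.

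**Working it through.** **The plan's own figures.** The documents give no figure for this rule and no withdrawal rate for the follow-up phases. The up-to-20% in Protocol 9.2 is an exclusion rate for the evaluable populations. The nearest safety figure is Protocol Table 5, which takes all 150 participants of a group as the denominator. It reproduces: 1 - (1-p)^150 = 0.139, 0.529, 0.779 and 0.952 at p = 0.1, 0.5, 1.0 and 2.0%, against 0.14, 0.53, 0.78 and 0.95 printed.

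**Inputs**
- r = 0.262 (MAE) and s = 0.011 (SAE), from Study B1971057 in Protocol 2.2.2.3. They cover a longer period than Intervals 8 or 9 and serve only as a scale.
- w = share withdrawn early: 2, 5 and 10%, assumed.
- Withdrawals have the same event risk as others, assumed. They are observed either for the whole interval or for half of it. The half-interval risk is h(x) = 1 - (1-x)^0.5, so h(0.262) = 0.1409 and h(0.011) = 0.0055.
- In the formulas below, a withdrawal is admitted if an MAE was reported.

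**Three readings of the sentence**

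1. *Restrictive (if).* AE-free withdrawals are left out. The same result follows if the table is taken to need information over the whole span and the sentence then adds back only withdrawals with an AE.
   - MAE, fully observed: r / [(1-w) + w·r]
   - MAE, half observed: [(1-w)·r + w·h(r)] / [(1-w) + w·h(r)]
   - SAE, fully observed: s / [(1-w) + w·r]
   - SAE, half observed: [(1-w)·s + w·h(s)] / [(1-w) + w·h(r)]

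2. *Precautionary.* All withdrawals enter. If none has information, the percentage is r·(1-w).

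3. *Redundant.* AE-free withdrawals with a safety contact already qualify under the table. The shift is zero.

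| Result | w = 2% | w = 5% | w = 10% |
|---|---|---|---|
| Restrictive, MAE, fully observed | 26.6% | 27.2% | 28.3% |
| Restrictive, MAE, half observed | 26.4% | 26.7% | 27.3% |
| Restrictive, SAE, fully observed | 1.12% | 1.14% | 1.19% |
| Restrictive, SAE, half observed | 1.11% | 1.12% | 1.14% |
| Precautionary, MAE, no information | 25.7% | 24.9% | 23.6% |

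On the restrictive reading the MAE shift runs from 26.41 - 26.2 = 0.2 point to 28.29 - 26.2 = 2.1 points. The SAE shift is at most 1.19 - 1.10 = 0.09 point.

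**Entry on any AE.** The sentence says any type of AE, which is wider than an MAE. With the 39.2% any-AE figure from the same study, the MAE percentage is r / [1 - w(1-0.392)] = 26.5, 27.0 and 27.9%. A simulation at N = 150 with 8 and 15 withdrawals gave 27.1% and 27.9%.

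**Count example.** Take N = 150 with 8 withdrawals, 2 of them with an MAE, and 37 MAEs among the 142 others. With everyone counted, 39/150 = 26.0% (95% CI 19.2-33.8, half-width 7.3 points). On the restrictive reading N = 150 - 6 = 144, and 39/144 = 27.1% (20.0-35.1).

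**Not every entrant raises a rate.** SAP 6.1.2.2 allows that nonserious AEs outside the three endpoints may be recorded during follow-up. Admitting one withdrawal with only such an AE moves an SAE rate from 2/142 = 1.41% to 2/143 = 1.40%. The rise holds in expectation only.

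**The case against.** The strongest reply is that the sentence includes and does not exclude. Nothing in the SAP says that an AE-free withdrawal is left out, the table already admits anyone dosed with available information, and Table 5 gives early withdrawals a start date with no AE condition. Read together, the sentence may add nothing. This stands as a possible reading, and it is why the shift may be zero. A reader might infer that the follow-up percentages are certainly inflated; the documents do not support that, because the precautionary reading would lower them. What remains is that the SAP does not say which reading applies.

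The exceptions to the withdrawal call do not settle the matter. A withdrawal with no contact and no event has no information for the interval and stays out under the table, and also under the rule proposed here. If such a person later reports an event, the report itself brings them in. Some AE-dependent entry therefore survives any rule based on available information.

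Nor is the proposed rule always more accurate. If withdrawals are half observed, it gives (1-w)·r + w·h(r) = 26.0, 25.6 and 25.0% at 2, 5 and 10% withdrawal, errors of -0.2, -0.6 and -1.2 points against 26.2%. The restrictive reading errs by +0.2, +0.5 and +1.1 points. The proposed rule gains accuracy only when withdrawals are more fully observed; fully observed, it returns 26.2%.

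It is also fair that Intervals 10 and 11 report the same endpoints over the whole 6 months on the Vaccination 1 and 2 safety populations, which this sentence does not govern. SAP 6.5.1 also allows, without requiring, listings of participants excluded from each population with reasons.

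**Conclusion.** The point holds in a limited form. Section 4 gives two statements of who belongs to the follow-up safety populations, and on the plain conditional reading one of them makes membership depend on the outcome. The MAE percentage would then be overstated by about 0.2 to 2.1 points at 2-10% withdrawal, and the SAE percentage by 0.1 point or less. At 5% withdrawal the MAE shift is about 1 point or less, small against a half-width of about 7 points. These sizes rest on assumed withdrawal, a borrowed event rate and equal risk in withdrawals.

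A reader might go on to infer a wrong safety conclusion. The documents do not support that: the study tests no hypotheses, no decision rule uses these percentages, and only Intervals 8 and 9 are touched. The change is worth making because the denominator of a primary safety summary is not uniquely specified and the remedy is short.

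**What to change.** Replace the sentence below the population table with: *Participants withdrawn early are included in the respective follow-up safety population if they received that vaccination and have any safety information (visit or telephone contact) covering any part of the follow-up interval, whether or not an AE was reported.* State the same rule in the definitions of follow-up safety populations 1 and 2.

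Add a footnote to Intervals 8 and 9 saying two things. Incomplete follow-up of withdrawals can understate risk; on the scale used here, by about 0.2 to 1.2 MAE points at 2-10% withdrawal if they are half observed. Withdrawals with no contact still enter only if an event is reported. The footnote can point to the follow-up withdrawal counts already planned in SAP 6.5.1.

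The sponsor could at the same time clarify the interval-start wording for early withdrawals in Table 5; the documents do not fix its meaning, and none is proposed here.

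The cost is one sentence used in three places, one programming rule and one footnote. No new data or tables are needed.

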#### **4.1. Vaccine Misallocation**

- Vaccinated but not randomized: These participants will be included in the safety population for safety analysis and will be reported under the vaccine group based on the vaccine received, but will be excluded from immunogenicity analyses.
- Randomized but not vaccinated: These participants will be included in the ITT population and excluded from any safety analyses. They may be included in the mITT populations if any assay results are available and will be reported under their randomized group for immunogenicity analyses.
- Randomized but received incorrect vaccine: These participants will be included in the mITT population for immunogenicity analyses if data are available and will be reported under the vaccine group based on the randomized vaccine. These participants will also be included in the safety population for safety analysis and will be reported under the vaccine group based on the vaccine received.

### **5. GENERAL METHODOLOGY AND CONVENTIONS**

#### **5.1. Hypotheses and Decision Rules**

There are no statistical hypotheses specified in the protocol. All safety and immunogenicity analyses will be descriptively summarized.

##### **5.1.1. Statistical Decision Rules**

Not applicable.

#### **5.2. General Methods**

Descriptive summary statistics will be provided for all endpoints. Unless otherwise explicitly stated, descriptive statistics for continuous variables are n, mean, median, standard deviation, minimum, and maximum. Descriptive statistics for categorical variables are the proportion (%) and the n (the numerator) and N (the denominator) used in the calculation of the proportion.

##### **5.2.1. Analyses for Binary Endpoints**

The number and percentage of participants in each category will be summarized. The 95% CI for percentages will also be presented, where appropriate. The 95% CI for the proportion will be constructed by the Clopper-Pearson method described by Agresti. The 95% CI will be presented in terms of percentages.

###### **5.2.1.1. Immunogenicity Data**

Each MenB ([Table 7](#)) and MenACWY ([Table 8](#)) strain has a validated LLOQ value defined.

**Table 7. Validated hSBA LOD and LLOQ for MenB Primary Strains**

Strain Type	Strain Variant	LOD	LLOQ
Primary	A22	1:4	1:16
	A56	1:4	1:8
	B24	1:4	1:8
	B44	1:4	1:8

Abbreviations: hSBA = serum bactericidal assay using human complement; LLOQ = lower limit of quantitation; LOD = limit of detection; MenB = *Neisseria meningitidis* group B.

**Table 8. Validated hSBA LOD and LLOQ for MenACWY Serogroups**

Serogroup	LOD	LLOQ
MenA	1:4	1:8
MenC	1:4	1:8
MenW	1:4	1:8
MenY	1:4	1:8

Abbreviations: hSBA = serum bactericidal assay using human complement; LLOQ = lower limit of quantitation; LOD = limit of detection; MenA, MenC, MenW, or MenY = *Neisseria meningitidis* group A, group C, group W, or group Y; MenACWY = *Neisseria meningitidis* groups A, C, W, and Y.

### 5.2.1.2. Safety Data

All safety endpoints will be summarized with percentages and 95% exact CIs (Clopper-Pearson method) for each group. The CIs presented for the safety data will not be used to test hypotheses but will be used to determine which events may need further clinical investigation.

